5.1 Treatment Plan

Radioembolization using SIR-Spheres Microspheres

Patients must be assessed with a hepatic angiogram and “break-through” scan to determine suitability for SIR-Spheres.

Hepatic Angiogram

The patient will undergo a preliminary angiogram of the liver to determine the vascular anatomy of the liver. The hepatic angiogram will provide a road map of the arterial supply of the liver in order to plan delivery of the SIR-Spheres microspheres. The hepatic angiogram should be performed together with the ‘break-through’ scan and results must be available prior to radioembolization with SIR-Spheres (see Appendix Appendix A/Appendix B).

Liver-Lung Break-Through Nuclear Scan

In order to mitigate the possibility of including patients who exhibit excessive liver-to-lung shunting a nuclear medicine ‘break-through’ scan using ^{99m}Technetium (Tc) macroaggregated albumin will be performed in all patients prior to SIR-Spheres treatment. Excessive liver-to-lung shunting resulting in radiation damage to the lungs has not been observed in any case of colorectal metastatic liver disease treated since the premarket approval (PMA) of SIR-Spheres microspheres for mCRC in 2003.

If either the hepatic angiogram or the liver-lung break through nuclear scan shows that a patient is ineligible to receive SIR-Spheres, then the patient will be removed from study and replaced.

SIR-Spheres Microspheres Administration

SIR-Spheres microspheres will be administered by a certified radiation oncologist, interventional radiologist, or nuclear medicine physician to the patient by injection through a trans-femoral catheter into the hepatic artery. All areas of tumor within the liver will be targeted with SIR-Spheres microspheres which usually involves treating both lobes of the liver. However, it is vital that the SIR-Spheres microspheres are not delivered to other organs such as the duodenum, stomach, pancreas etc.

If the metastases are limited to only one lobe, the radiologist can insert the catheter selectively into the lobar artery supplying only that lobe that contains the metastases. The SIR-Spheres microspheres will then be delivered only to the lobe containing the metastases with sparing of the other normal lobe. The SIR-Spheres microspheres are injected slowly into the hepatic artery to avoid reflux back down the hepatic artery and placement in the pancreas, stomach and other organs.

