7.2 Patient Assessment for SIR-Spheres

Cohort 1 and Cohort 2 patients will be assessed to determine suitability for SIR-Spheres.

The following tests will be obtained 7-4 days prior to SIR-Spheres treatment.

- **Hepatic angiogram**
- **99m Tc MAA lung shunt scan**

Cohort 1 patients will have these assessments performed during week 4 prior to SIR-spheres treatment.

Cohort 2 patients will be assessed at Screening 7-4 days prior to SIR-Spheres treatment on CID1.

7.3 Study Treatment Assessments - COHORT 1

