10.3 Analysis Population

The following analysis populations will be used:

- Intent-To-Treat Population (ITT) is defined as all patients who have started study treatment (Radioembolization with SIR-Spheres ^{90}Y or regorafenib).
- Safety Population is defined as all patients who have received at least one dose of study treatment. In this instance, the ITT and safety populations would consist of the same patients.

CONFIDENTIAL

STUDY DEVICE: SIR-Spheres®

SCRI INNOVATIONS STUDY NUMBER: GI 189

DATE OF ORIGINAL PROTOCOL: 16 December 2013

Date of Amendment #1: 15 April 2014

Version 2.0

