10.4.4 Safety Analysis

Safety will be assessed through the analysis of the reported incidence of treatment-emergent AEs. Treatment-emergent AEs are those with an onset on or after the initiation of therapy, and will be graded according to NCI CTCAE v 4.03. A copy of CTCAE scoring system may be downloaded from: http://evs.nci.nih.gov/ftp1/CTCAE/CTCAE_4.03_2010-06-14_QuickReference_8.5x11.pdf. AEs that occur prior to initiation of therapy (after consent is signed, i.e. during mapping for SIR-Spheres treatment), will also be assessed.

The AEs will be coded using Medical Dictionary for Regulatory Activities (MedDRA), and summarized using system organ class and preferred term by cohort for all patients in the Safety Population. In addition, summaries of SAEs, AEs leading to treatment discontinuation, AEs by maximum NCI CTCAE grade, and AEs related to study treatment will also be presented by treatment cohort.

Other safety endpoints including laboratory results will be summarized for all patients in the Safety Population.

Concomitant medications will be coded using the World Health Organization-Drug Dictionary and they will be listed and summarized by treatment cohort.

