11.1.5 Recording and Reporting of Adverse Events

Recording of Adverse Events

All AEs of any patient during the course of the research study will be recorded in the eCRF, and the investigator will give his or her opinion as to the relationship of the AE to the study material or process (i.e., whether the event is related or unrelated to study drug administration, SIR-Spheres microspheres or SIRT procedure).

All AEs should be documented. A description of the event, including its date of onset and resolution, whether it constitutes a serious adverse event (SAE) or not, any action taken (e.g., changes to study treatment), and outcome, should be provided, along with the investigator’s assessment of causality (i.e., the relationship to the study treatment[s]). For an AE to be a suspected treatment-related event there should be at least a reasonable possibility of a causal relationship between the protocol treatment and the AE. Adverse events will be graded according to the NCI CTCAE v4.0, and changes will be documented.

If the AE is serious, it should be reported immediately to SCRI Innovations Safety Department. Other untoward events occurring in the framework of a clinical study are to be recorded as AEs (i.e., AEs that occur prior to assignment of study treatment that are related to a protocol-mandated intervention, including invasive procedures such as biopsies, medication washout, or no treatment run-in).

Any clinically significant signs and symptoms; abnormal test findings; changes in physical examination; hypersensitivity; and other measurements that occur will be reported as an AE, and collected on the relevant eCRF screen.

CONFIDENTIAL

STUDY DEVICE: SIR-Spheres®

SCRI INNOVATIONS STUDY NUMBER: GI 189

DATE OF ORIGINAL PROTOCOL: 16 December 2013

Date of Amendment #1: 15 April 2014

Version 2.0

Test findings will be reported as an AE if: the test result requires an adjustment in the study drug(s) or discontinuation of treatment, and/ or test findings require additional testing or surgical intervention, a test result or finding is associated with accompanying symptoms, or a test result is considered to be an AE by the investigator.

CONFIDENTIAL

STUDY DEVICE: SIR-Spheres®

SCRI INNOVATIONS STUDY NUMBER: GI 189

DATE OF ORIGINAL PROTOCOL: 16 December 2013

Date of Amendment #1: 15 April 2014

Version 2.0

Reporting Period for Adverse Events

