Final Analysis	6 months after last patient has been recruited into study
1.5 Responsibilities	
Trial Statistician:	Development of SAP and shells Review deliverables presented by statistical programmers
PK Statistician:	N/A
Independent Statistician:	N/A

1.6 Analysis Software	
Main statistical analysis:	SAS Version 9.3 or above
Other analysis software:	None

1.7 Coding	
 Adverse Events  Medical History	 MedDRA:  Version  Most current release and update coding with new major releases  NCI-CTCAE Version
 Concomitant Medication  Prior Therapy  Subsequent/Further Therapy	 WHO-Drug:  Version  Most current release and update coding with new major releases
3 Analysis Population	
Intent-To-Treat (ITT) Population definition:	 All patients who have started treatment in the study  All patients who have been randomized in the study, regardless of whether they have received any treatment or not  All patients who have been randomized and have started treatment in the study  Other definition, specify:
Per Protocol (PP) Population to be used in analysis:	 Yes  No If yes, please specify the criteria for exclusion from the PP population:
Safety (SAF) Population definition	 All patients who have started treatment in the study. Patients will be analyzed according to the actual treatment they have received.  Other definition, specify:
Other Analysis Population definition:	N/A
4 Baseline Value Definitions	
	Last value prior to first date of study drug treatment
5/6 Efficacy	
Response Criteria Used:	 RECIST 1.0  RECIST 1.1  Cheson 2007  Modified RECIST – specify:  Other criteria, Specify:

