 Early Progression Rate (EPR)			
 Time To Progression (TTP)	Default: Estimates of medians in each treatment arm		
 Progression-Free Survival (PFS)	 Other quartiles or percentages of survival required, specify: probability evaluated at 6 month intervals		
 Overall Survival (OS)	 Hazard ratio & 95% confidence interval between treatment arms, unstratified		
 Duration of Response	 p-value, specify statistical test:		
 Duration of Stable Disease	 Hazard ratio & 95% confidence interval between treatment arms, stratified (specify stratification factor(s)):		
 Time To Treatment Failure (TTF)	 p-value, specify statistical test:		
 Other, Specify:			
7 Safety			
Adverse Events	Definition of Treatment-Emergent Adverse Event (TEAE): any adverse event (AE) that starts or worsens after the start of the first dose of study treatment up to 30 days post last dose.		
Laboratory Data	Data will be summarized by:  NCI-CTCAE for CTCAE-gradable parameters, and H/L for non-CTCAE-Gradable parameter		

H/L for all lab parameters

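### AEs of the SIR-Spheres mapping procedure are treatment-emergent in Cohort 1 but in Cohort 2 only if they worsen after first dose, and the plan does not ensure that they are recorded and tabulated alike

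*Protocol*

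**What the plan says.** **Mapping and replacement.** Protocol 5.1 applies one rule to both cohorts: if either the hepatic angiogram or the liver-lung scan "shows that a patient is ineligible to receive SIR-Spheres, then the patient will be removed from study and replaced". The timing in Protocol 7.2 differs: "Cohort 1 patients will have these assessments performed during week 4 prior to SIR-spheres treatment", whereas "Cohort 2 patients will be assessed at Screening 7-4 days prior to SIR-Spheres treatment on CID1".

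**Analysis sets.** Protocol 10.3: "Safety Population is defined as all patients who have received at least one dose of study treatment". The ITT set is defined by the start of either treatment, and the protocol notes that the two sets contain the same patients. SAP Section 3 agrees and adds: "Patients will be analyzed according to the actual treatment they have received".

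**Treatment-emergent window.** Protocol 10.4.4 uses onset once therapy has begun. SAP Section 7 takes any AE that "starts or worsens after the start of the first dose of study treatment up to 30 days post last dose".

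**AEs before first treatment.** Protocol 10.4.4: "AEs that occur prior to initiation of therapy (after consent is signed, i.e. during mapping for SIR-Spheres treatment), will also be assessed". Protocol 11.1.5 also asks sites to record as AEs those "AEs that occur prior to assignment of study treatment that are related to a protocol-mandated intervention", and names invasive procedures among these. Against this, the reporting-period part of 11.1.5 and Section 11.2 start the AE and SAE periods at study treatment.

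**Visits and outputs.** Cohort 1 Day 22 (7.3.4), the mapping visit, lists an AE assessment. The Cohort 2 baseline (7.4.1) and Day 1 (7.4.2) list none; the first is on Day 8 (7.4.3). SAP Table 8, the only AE table, covers treatment-related AEs in the Safety set.

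**The concern.** Safety is the primary objective, and the protocol describes the study as a comparison of safety between the two sequences. Both cohorts undergo the same mapping procedure. A reader setting the AE tables side by side would assume that its complications were counted by the same rule, and under the written definitions they are not.

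Two things are at stake. The first is classification: events of one procedure sit inside the window in one cohort and mostly outside it in the other. Patients who fail mapping likewise enter the denominator in one cohort only. The second is recording. If sites work from the reporting periods in 11.1.5 and 11.2 and from the Cohort 2 visit list, some mapping AEs or SAEs in that cohort may not be captured. A table can be re-cut later, but an unrecorded event cannot be recovered at analysis.

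**Working it through.** **1. The plan's own figure.** The only precision statement (Protocol 10.2) is 21% for the response rate with 25 patients. The exact Clopper-Pearson half-width is largest at 12/25 or 13/25, at 20.4 points, so the figure holds as a half-width. It is not disputed here and serves as a yardstick for sampling error.

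**2. Timeline.** For Cohort 1, Protocol 1.2 gives three weeks of regorafenib and a one-week hold.

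| | Cohort 1 | Cohort 2 |
|---|---|---|
| First dose | Day 1 (regorafenib) | Day 1 (SIR-Spheres) |
| SIR-Spheres | Day 29 | Day 1 |
| Mapping, 7-4 days earlier | Days 22-25 | 7-4 days before Day 1 |
| Mapping inside the treatment-emergent window? | Yes | No, unless the AE worsens after first dose (SAP) |
| Mapping failure in Safety/ITT? | Yes, dosed with regorafenib | No, never dosed |

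A Cohort 1 patient who fails mapping and takes no further dose has a window to day 21 + 30 = 51, so an AE arising at mapping is still inside it. The order does not depend on the exact SIR-Spheres day, because Cohort 1 mapping always follows the first regorafenib dose.

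**3. Size of the AE effect.** The documents give no mapping-AE rate, so every rate below is an assumption. Let m be the chance of a mapping AE per mapped patient and q the any-AE rate from all else, equal in both cohorts and independent of m. The expected number in 25 patients is 25m, and P(at least one) = 1 − (1 − m)^25. The Cohort 1 rate becomes 1 − (1 − m)(1 − q); Cohort 2 stays at q.

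| m | 25m | P(at least one) | q = 30% | q = 60% | q = 90% |
|---|---|---|---|---|---|
| 2% | 0.5 | 39.7% | 31.4% | 60.8% | 90.2% |
| 4% | 1.0 | 64.0% | 32.8% | 61.6% | 90.4% |
| 8% | 2.0 | 87.6% | 35.6% | 63.2% | 90.8% |

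Protocol 8.1.3 says that mild fever affects most patients after radioembolization. For AEs of any kind the two right-hand columns are therefore the more realistic, with shifts of 0.2 to 3.2 points. The 30% column suits a narrower event class. For comparison, the 95% interval is 14.9% to 53.5% for 8/25 and 38.7% to 78.9% for 15/25. An extreme case, m = 20% on q = 20%, gives 1 − 0.8 × 0.8 = 36%. That 16-point gap approaches the 16.9-point half-width at 5/25.

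**4. Size of the denominator effect.** Suppose k Cohort 1 mapping failures are replaced, 30% of the 25 SIR-Spheres patients have some event, and a proportion r of the failures do. The Cohort 1 rate is (0.30 × 25 + r × k)/(25 + k). For k = 2, 4, 6:

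- r = 0: 27.8%, 25.9%, 24.2%
- r = 30%: 30.0% throughout
- r = 50%: 31.5%, 32.8%, 33.9%

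The direction depends on r, which is unknown. The same set feeds the ORR difference planned in the SAP. At an assumed 10% failure rate, 25/0.9 rounds up to 28. Five responders then give 5/28 = 17.9% (95% CI 6.1% to 36.9%) in Cohort 1, against 5/25 = 20.0% (6.8% to 40.7%) in Cohort 2.

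**5. Recording.** Section 10.4.4 and the recording part of 11.1.5 point to capture during mapping. The reporting-period part of 11.1.5, Section 11.2 and the Cohort 2 visit list point to a start at treatment. No arithmetic settles this; the texts have to be aligned.

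**The case against.** The strongest reply is that the passages can be read together. The reporting period in 11.1.5 governs AEs regardless of relationship. The recording rule adds a narrower class before treatment, into which a protocol-required angiogram falls, and 10.4.4 names mapping outright. The same part of 11.1.5 asks for serious AEs to be reported at once. Much of this stands: a reader might infer that Cohort 2 mapping AEs are left out altogether, and the documents do not support that. What remains is that 11.2 still starts SAEs at study treatment, the Cohort 2 baseline prompts no AE assessment, and no planned table receives the events.

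Nor is the Safety set wrong. A patient who took regorafenib belongs in it and an undosed patient does not. Cohorts enrol one after the other and summaries are by cohort, so a Cohort 1 patient given regorafenib alone would hardly be shown under Cohort 2.

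Much of the disposition is also planned. Protocol 10.4.1 counts patients screened, treated and withdrawn by cohort. The SAP exposure table counts patients with SIR-Spheres activity, so subtraction shows who never received it. It does not separate mapping failures from other early stops, and the reasons listed in Protocol 3.3 do not name mapping ineligibility, although 5.1 does provide for removal on that ground.

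Finally, investigators attribute events to drug, microspheres or procedure. A mapping AE therefore need not reach SAP Table 8, and the illustrated shifts fit the broader treatment-emergent summaries in Protocol 10.4.4 better.

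**Conclusion.** The asymmetry follows directly from the definitions: mapping AEs are treatment-emergent in Cohort 1 and, unless they worsen after first dose, not in Cohort 2. Replaced mapping failures stay in the analysis sets in Cohort 1 only. Cohort 2 mapping AEs may be under-recorded and, as planned, would not be tabulated beside those of Cohort 1.

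The effect cannot be sized, or given a net direction, from the documents. Under the assumed 2% to 8% mapping-AE rates the shift is 0.2 to 5.6 points, depending on the base rate. This is probably within sampling error at 25 per cohort, in a non-randomised study with no formal test.

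Two stronger readings should be resisted. One is that the safety comparison is biased in a known direction; step 4 of the working shows that it could go either way. The other is that data will certainly be lost. That depends on which passage sites follow, and the documents do not say. The case for change rests on treating the same procedure alike in both cohorts and on the fact that unrecorded events cannot be recovered.

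**What to change.** 1. **Protocol.** Reconcile the reporting period in 11.1.5 and Section 11.2 with 10.4.4 and the recording rule in 11.1.5, so that AE and SAE recording covers the mapping procedure in both cohorts. This helps only while Cohort 2 patients remain to be mapped; the documents do not give enrolment status.
2. **SAP, AEs.** Keep the Safety set. Add one by-cohort table of AEs from mapping up to SIR-Spheres, or study exit, in all mapped patients, classified identically in both cohorts. A note should say that Cohort 1 patients have by then taken regorafenib, so the comparison is descriptive.
3. **SAP, disposition.** Add by-cohort rows to the planned summaries for mapping failures and for patients who received only one modality.

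A by-cohort AE summary of SIR-Spheres-treated patients, counted from the SIR-Spheres date, is an optional supplement. It leaves out the first regorafenib cycle of Cohort 1, so it cannot replace the overall tables.

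Cost: a short protocol clarification, one extra table and a few extra rows. No analysis set changes.

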5.2 Treatment Duration

Patients will be evaluated for toxicity at the start of each 28-day cycle of regorafenib. Patients will be restaged at 6 weeks and 12 weeks after SIR-Spheres in both cohorts, and every 8 weeks thereafter, with imaging, laboratory chemistries, and tumor markers as defined in Appendix A and Appendix B**Error! Reference source not found.** Patients will continue on treatment until progression as defined in Appendix C or intolerance to side effects.

5.3 Concomitant Medications

Patients will be instructed not to take any additional medications during the course of the study without prior consultation with the research team. At each visit, the patient will be asked about any new medications he is taking or has taken after the start of the study drug.

5.3.1 Permitted Concomitant Medications

Premedication with anti-emetics is allowed according to standard practice guidelines. At each visit, the patient will be asked about any new medications he is taking or has taken after the start of the study drug.

All concomitant medications and significant non-drug therapies taken \leq 14 days prior to the start of study drug should be recorded.

Medications may be administered for maintenance of existing conditions prior to study enrollment or for a new condition that develops while on study, including but not limited to the following:

- Use of bisphosphonates and receptor activator of nuclear factor kappa-B ligand

CONFIDENTIAL

STUDY DEVICE: SIR-Spheres®

DATE OF ORIGINAL PROTOCOL: 16 December 2013

Date of Amendment #1: 15 April 2014

SCRI INNOVATIONS STUDY NUMBER: GI 189

Version 2.0

(RANKL) inhibitors like denosumab. Treatment with these agents must begin 1 day prior to study treatment or after treatment is initiated. Treatment with these agents cannot be initiated on Cycle 1 Day 1.

- Full dose Coumadin is allowed if required for the treatment of thromboembolic disease occurring after the patients have initiated study treatment. INR must be followed and managed on Day 1 and 15 of each treatment cycle.
- Low molecular weight heparin is allowed.
- Erythropoietic and granulocyte colony-stimulating factor (G-CSF) agents according to standard guidelines. Neutropenia/fever should be managed according to accepted guidelines.

Other medications considered necessary for the patient's safety and well-being may be given at the discretion of the investigator with the exception of those listed in Section 5.3.2.

5.3.2 Prohibited Concomitant Medications

The following treatments are prohibited while in this study:

- No other investigational therapy should be given to patients. No anticancer agents other than the study medications should be given to patients. If such agents are required for a patient, then the patient must first be withdrawn from the study.
- Avoid concomitant use of strong CYP34A inducers (e.g., rifampin, phenytoin, carbamazepin, phenobarbital, and St John's wort). For the most updated information, visit the following website: <http://medicine.iupui.edu/clinpharm/ddis/>. (see Appendix G)
- Avoid concomitant use of strong CYP34A inhibitors (e.g., clarithromycin, grapefruit juice, itraconazole, ketoconazole, posaconazole, telithromycin, and voriconazole). For the most updated information, visit the following website: <http://medicine.iupui.edu/clinpharm/ddis/> (see Appendix G)
- Herbal preparations/medications are not allowed throughout the study. These herbal medications include, but are not limited to: St. John's wort, kava, ephedra (ma huang), gingko biloba, dehydroepiandrosterone (DHEA), yohimbe, saw palmetto, and ginseng. Patients should stop using these herbal medications 7 days prior to first dose of regorafenib.

5.4 Correlative Studies

Blood samples for biomarker testing will be collected from all patients prior to the hepatic angiogram and 99m Tc MAA lung shunt scan, which will be obtained 7-4 days prior to SIR-Spheres treatment (see Section 7.2), on Day 8 after SIR-Spheres treatment, and Day 30 (pre-dose) after SIR-Spheres treatment. Expressions of cytokines and proteins will be measured to explore potential biomarkers that may correlate with clinical outcome.

Cytokine analyses will include, but not be limited to, the following: VEGFA, VEGFC, VEGFD, FGF2, HGF, EGF, PDGF-AA, PDGF-AB/BB, MMP-9, sVEGFR-2, E-selectin, VCAM-1, ICAM-1, MIF, TNF α , IFN- α and - γ , LIF, TGF- α , TGF- β 1, Angiopoietin-2, Endoglin, IGF, Osteopontin, GM-CSF, G-CSF, M-CSF, SCGF- β , SCF, Beta-NGF, PIGF, MCP-1, MCP-3,

CONFIDENTIAL

STUDY DEVICE: SIR-Spheres®

SCRI INNOVATIONS STUDY NUMBER: GI 189

DATE OF ORIGINAL PROTOCOL: 16 December 2013

Date of Amendment #1: 15 April 2014

Version 2.0

RANTES, MIP-1 α , MIP-1 β , MIG, Eotaxin, IP-10, SDF-1 α , GRO- α , CTACK, IL-1 β , IL-2, IL-3, IL-4, IL-5, IL-6, IL-7, IL-8, IL-9, IL-10, IL-12 p40, IL-12 p70, IL-16, CA9 and HIF-1 alpha.

Protein expression in blood samples will be measured by proteomics platform.

